3.3 PREVIOUS AND CONCOMITANT MEDICATIONS

Any medication the patient takes other than the study drug, including herbal and other non-traditional remedies, is considered a concomitant medication. The following information must be recorded in the eCRF for each concomitant medication: generic name, route of administration, start and stop dates (month and year at minimum), dosage, and indication. Any changes in the dose or regimen of a concomitant medication must also be recorded in the eCRF.

At the Screening visit, patients/caregivers will be asked what medications the patient has taken during the last 30 days. At each subsequent study visit, patients/caregivers will be asked what concomitant medications the patient is currently taking or has taken since their last visit.

Use of rescue medication (Dulcolax®) will be recorded daily in the BM Diary and should not be included under concomitant medications.

3.3.1 Permitted Concomitant Medications

Rescue Medication (RM) – Dulcolax®

Dulcolax® 5 mg tablets will be dispensed to patients at Visit 1 and resupplied as needed. From Visit 1 and for the duration of the trial, only protocol supplied Dulcolax® is to be used as the “rescue medication” (laxative) - no other laxatives are allowed. The study level allowable dosage for children age 6 to 12 years is one tablet (5 mg daily) and for children 12 years and older the dosage is 1 to 2 tablets daily (5 to 10 mg). Dulcolax® tablets must be swallowed whole.

Patients are instructed to take rescue medication only if it has been at least 72 hours since their last bowel movement. A patient is therefore expected to have no more than two days of RM use in any given week.

Each rescue medication usage will be recorded daily via the electronic diary. Clinical site personnel will review rescue medication use with patients/caregivers during their telephone contact visits and have the option to discontinue participation of patients who do not adhere to rescue medication guidelines.

Patients are advised NOT to take rescue medication for the period from 24 hours before to 72 hours after Day 1 of dosing. This avoids confounding the data collected in the first week of study drug administration and allows for accurate determination of the time to first BM. Dulcolax®. An initial supply of Rescue Medication will be provided to each site from [REDACTED]. For additional bulk supplies of rescue medication, the site will make a request through IWRS. Supplies of Dulcolax® will not be reconciled at the completion of the study. Sites must track inventory of rescue medication supplies as this will not be managed through IWRS.

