19. Patient reports having more than 1 loose, mushy stool (Diary-recorded stool consistency of 6 on the Bristol Stool Form Scale (BSFS or 4 on the modified Bristol Stool Form Scale for Children [mBSFS-C]) or any watery stool (Diary-recorded stool consistency of 7 on the BSFS or 5 on the mBSFS-C) with any SBM that occurred in the absence of laxative use on the calendar day of the BM or the calendar day before the BM during each 7-day (week) period before the randomization day and up to the day of randomization;
20. ≥ 3 CSBMs per week for either week of the 2-week baseline diary assessment immediately preceding the randomization visit;
21. > 6 SBMs per week for either week of the 2-week baseline diary assessment immediately preceding the randomization visit;
22. Patient reports worst abdominal pain intensity (WAPI) scores in the 2-week baseline diary that meet either of the following:
 - a. WAPI score of 0 on the 11-point Numeric Rating Scale or Wong-Baker Faces® Pain Rating Scale for more than two days during each week of the 2-week baseline diary period.
 - b. An average WAPI < 3 for either of the two weeks of the baseline diary;

23. Completion of < 5 of the 7 required daily diary entries in each week of the 2-week baseline diary assessment immediately preceding the randomization visit;
24. Use of rescue medication (Dulcolax®, bisacodyl) for more than 2 days during either of the two weeks of the 2-week baseline diary assessment immediately preceding the randomization visit.

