5.2.2 Visit 2: Randomization (Day 1)

Continued study eligibility must be confirmed ***prior to randomization***, including the following:

- Verify Non-Diary eligibility:
 - Review inclusion and exclusion criteria
 - Confirm that patient has used only study-supplied rescue medication laxative (Dulcolax®) since Visit 1
 - Confirmation that patient is on a stable diet and has no significant changes in their consumption of liquids or fiber or their level of activity
 - Perform urine drug screen (a positive test results in automatic screen failure)
 - Perform urine pregnancy test, if applicable (a positive test results in automatic screen failure)
- Update medical history and concomitant medications, as necessary.
- Log into IWRS to obtain system-generated diary eligibility based on the previous 14 days of daily diary entries before randomization. (Only patients who demonstrated diary and RM compliance will be considered diary eligible. **The PI or site staff will not be responsible for evaluating diary data to make the diary-based eligibility determination.**
- Ineligible patients, as determined by the IWRS, will be screen-failed.
- For diary eligible patients, as determined by the IWRS, confirm patient continues to meet all other eligibility criteria and access IWRS to randomize the patient and obtain the study drug kit number.
- The following procedures will be performed ***prior to study drug dosing for patients eligible for randomization***:
- Symptom-directed physical examination and vital signs (body temperature and seated blood pressure, heart rate, respiration rate)
- Assessment of adverse events
- Patient/caregiver to complete all baseline PRO questionnaires (Per Study Procedure Manual) prior to any blood collections
- Collection of blood and urine samples for safety laboratory assessments (hematology, serum chemistry, urinalysis)
- Collection of blood samples for plecanatide/SP-338 concentration assessments (see **Section 4.3.3** for details)
- Selection of drug kit(s) as per the IWRS-generated report
- Supervision of administration of first dose of study drug from the assigned study drug kit(s)
- Recording of time of dosing

The following procedures will be performed ***after study drug dosing***:

- At selected sites and in a subgroup of patients who consented to an additional PK analysis, blood samples will be obtained for PK assessment 30, 60, 90 and 120 minutes after study drug administration

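### Section 3.3.1 gives 12-year-olds two daily rescue limits, and its two-days-a-week figure does not follow from the 72-hour rule, so a patient who obeys that rule can fail screening under exclusion 24

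*Combined protocol and SAP*

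**What the plan says.** Protocol section 3.3.1 (Permitted Concomitant Medications) sets the daily Dulcolax allowance in one sentence, which reads in part: "for children age 6 to 12 years is one tablet (5 mg daily) and for children 12 years and older the dosage is". The amount then given for the older band is one to two tablets a day, or 5 to 10 mg. Everywhere else the protocol and SAP divide patients into 6 to 11 years and 12 to under 18 years (synopsis; protocol section 1 and Table 3; SAP sections 3.2 and 3.3.1).

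The next paragraph of section 3.3.1 tells patients to "take rescue medication only if it has been at least 72 hours since their last bowel movement". Protocol section 4.3.8 and SAP section 3.3.7 repeat the 72-hour condition. Section 3.3.1 then draws a consequence: "A patient is therefore expected to have no more than two days of RM use in any given week".

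The two-day figure reappears as an eligibility test. Exclusion 24 (section 3.2) removes anyone who uses rescue "for more than 2 days during either of the two weeks of the 2-week baseline diary assessment". Section 5.2.2 describes the system-generated eligibility check in terms of conduct: "Only patients who demonstrated diary and RM compliance will be considered diary eligible". The site does not make that determination itself. The synopsis uses similar terms: proper use of rescue is among the eligibility items confirmed from the diary, and non-compliance with rescue use is a key exclusion.

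**The concern.** There are two separate faults in a paediatric dosing and eligibility text.

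First, the two dose clauses share age 12 and give different daily maxima, so sites can apply different limits to patients of the same age. Age 12 matters here because it is the boundary between the trial's two groups, with a special rule for children expected to turn 12 before randomisation (section 4.1.1). The number of rescue tablets is also a tested secondary endpoint (protocol section 8.8.2.5; SAP section 5.2.4.5).

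Second, the text presents two days a week as the result of obeying the 72-hour rule. If the rule in fact permits more, exclusion 24 rejects some patients who did what they were told, and the surrounding wording records them as non-compliant. These would tend to be children with long gaps between BMs or a poor response to rescue. Reasons for screen failure are documented and tabulated (protocol section 5.2.1; SAP section 5.1.1), so the label would carry into the report.

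**Working it through.** **Age bands.** Apply both clauses of section 3.3.1 to each whole year of age:

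| Age | First clause, daily maximum | Second clause, daily maximum |
|---|---|---|
| 6 to 11 | 5 mg | does not apply |
| 12 | 5 mg | 10 mg |
| 13 to 17 | does not apply | 10 mg |

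Age 12 is the only year under both clauses. The maxima differ by a factor of 10/5 = 2.

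**Reproducing the two-day figure.** A week has 7 × 24 = 168 hours, and 168/72 = 2.33, which rounds down to 2. The documents do not show how two was reached, but this simple division gives it. It counts whole 72-hour intervals, not the largest number of permitted dosing days.

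**Case 1: every dose produces a BM.** Let the first dose be at clock hour t on day 1 of the week, and let each BM follow its dose by L hours. The next dose is permitted 72 hours after that BM. The permitted dose times are then t, t + 72 + L and t + 144 + 2L. The third falls within the week if t + 144 + 2L < 168, that is, if L < 12 − t/2.

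| First dose | Three days permitted if L is below |
|---|---|
| 00:00 | 12 h |
| 07:00 | 8.5 h |
| 08:00 | 8 h |
| 12:00 | 6 h |
| 20:00 | 2 h |

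Example with t = 8 and L = 6: dose on day 1 at 08:00, BM at 14:00; dose on day 4 at 14:00, BM at 20:00; dose on day 7 at 20:00. The third dose is at hour 8 + 144 + 12 = 164, before 168. The documents give no figure for L, so this case depends on an assumption. Two days is the maximum only if every dose works and takes 12 hours or more.

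**Case 2: a dose produces no BM.** The 72 hours run from the last BM, which has not changed, so the condition is still met the next day. The allowance is stated per day and no minimum interval between doses is given. For a first dose at 08:00 on day 1:

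- One failed dose in the week: day 1 fails, day 2 at 08:00 works with a BM at 14:00, and the next dose is permitted on day 5 at 14:00. That is three days.
- One failed dose in every episode: days 1, 2, 5, 6 (L from 0 to 12 h) or 1, 2, 6, 7 (L = 24 h). That is four days.
- Two failed doses in every episode: days 1, 2, 3, 6, 7 (L from 0 to 12 h) or 1, 2, 3, 7 (L = 24 h). That is five or four days.
- No BM all week: seven days.

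The conclusion in Case 2 does not hang on any particular L.

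**Against exclusion 24.** Any of these patterns in a baseline week exceeds two days. One qualification applies: section 3.3.1 also advises against rescue from 24 hours before Day 1 of dosing. Day 7 of the second baseline week is the day before Day 1, so the day 1, 4, 7 pattern fits the first baseline week only. The day 1, 2, 5 pattern fits either week.

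**The case against.** The dose clause can be read charitably. The first band may mean up to the twelfth birthday, which would match the trial's groups, and one tablet satisfies both clauses, so only the maximum is in doubt. Sites are blinded and randomisation is within age group, so nothing suggests that the limit would be applied differently by arm. All of that stands, but it does not remove the contradiction from a dosing instruction, and no other section resolves it.

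It can also be said that exclusion 24 is worded as a limit on use, which a sponsor may set for its own reasons. That is fair to exclusion 24 alone. The compliance wording comes from the synopsis and section 5.2.2, and section 3.3.1 offers the figure as a deduction, not as a separate limit.

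A reader might go further. Sites "have the option to discontinue participation of patients who do not adhere to rescue medication guidelines", and weeks without BM data after withdrawal are scored as zero spontaneous BMs (protocol section 8.4.1; SAP section 3.3.4). From this one could infer that rule-following patients, more of them on placebo, are discontinued after randomisation and that the drug effect is exaggerated. The documents do not support that:

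- After randomisation two days is only expected. Discontinuation is a site option, and no section ties it to a count of days.
- The advice against rescue until 72 hours after Day 1 rules out the day 1, 4, 7 pattern in treatment Week 1. Only repeated failed doses could exceed two days in that week.
- A BM within 24 hours of a laxative is not spontaneous under the protocol's definition. The BMs in the Case 1 example would not count in the primary endpoint anyway, so scoring similar weeks as zero would change little.
- The documents give no rate from which to calculate a shift.

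**Conclusion.** Both faults stand as written.

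- **Age 12:** two daily maxima that differ twofold. The number of patients affected is not known, because no age distribution is given. An even spread over ages 12 to 17 would put 120/6 = 20 adolescents at age 12. That is an assumption, the possible range is 0 to 120, and the point does not depend on it.
- **Two days a week:** the 72-hour rule permits three days when every dose works quickly enough, three or more once a dose fails, and up to seven. The first of these needs an assumed time to BM; the others rest only on the rule as stated and the absence of a minimum interval between doses.

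A patient can therefore follow the 72-hour instruction exactly, meet exclusion 24 and be recorded as non-compliant. That reading takes exclusion 24 to be what the eligibility system applies as rescue compliance; it is the only rescue criterion among the diary-based exclusions. How often this would happen cannot be derived from the documents.

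The exclusion acts before randomisation, so it affects who enters the trial and how screen failures are described, not the comparison between arms.

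**What to change.** The sponsor should:

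1. Reconcile the two age clauses in section 3.3.1 so that each age has one stated limit. Which limit applies at age 12 is the sponsor's decision.
2. Reconcile four statements with one another: the 72-hour rule (3.3.1, 4.3.8, synopsis, SAP 3.3.7), the two-day sentence (3.3.1), exclusion 24 (3.2) and the rescue-compliance wording (synopsis, 5.2.2). The text should make clear whether two days is a deduction, an expectation or a separate limit, and what the eligibility system tests. The choice of rule is the sponsor's.

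The cost is a few sentences in the protocol and a memo to sites. The eligibility programming needs checking only if exclusion 24 itself changes. Sample size, visits and planned analyses are unaffected.

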3.3.2 Prohibited Prior and Concomitant Medications and Supplements

The following medications, laxatives, and supplements are **prohibited within 15 days** prior to the Screening visit and for the duration of the study, unless otherwise indicated:

- Oral anticholinergic agents (topical and inhaled anticholinergics are allowed)
- Drugs with activity at the 5-HT4, 5-HT3, and 5-HT2b receptors
- Antidiarrheal agents including Pepto Bismol™, kaolin, and opiates

- Drugs known to cause diarrhea such as orlistat, acarbose, misoprostol, and colchicine
- Bile acid sequestrants (cholestyramine and colestipol)
- Amitiza® (lubiprostone)
- Linzess®/Constella® (linaclotide)
- Resolor® (prucalopride) antibiotics, including rifaximin, and opioids, including tramadol or opiate antidiarrheals (diphenoxylate, and loperamide) are generally prohibited. However, short-term (< 15 days) use of opioids or antibiotics for the treatment of AEs or intercurrent illness may be administered during the Screening Period prior to Visit 2 (Day 1) or after randomization in the study as long as they are reported. If a patient needs to be started on an antibiotic or a narcotic during the Screening Period, the patient's Visit 2 may be delayed allowing for discontinuation of these medications at least 3 days before randomization.

Prohibited drugs when required and used to treat TEAEs are allowed. The following drugs are allowed only if the patient has been on a **stable dose for the 8 weeks** prior to the Screening/Baseline Period and the patient agrees to remain on this dose for the duration of the study.

- Anticonvulsants
- Antidepressants
- Calcium channel blockers
- Proton pump inhibitors and H2 antagonists
- Antihistamines that have primarily anti H1 activity (e.g., cetirizine, loratadine, and chlorpheniramine)
- Bulking agents (e.g., psyllium [Metamucil®] methylcellulose [Citrucel®], calcium polycarbophil)

Thyroid hormone supplementation: levothyroxine (T4) or natural desiccated thyroid hormone or liothyronine (T3) are allowed only if the patient has been on a stable dose for the 30 days prior to the 4-week Screening/Baseline Period and remains on this dose for the duration of participation in the study. TSH level will be determined at screening to determine eligibility (T3 and free T4 will only be tested if TSH is out of range).

Prohibited Laxatives

All laxatives (except for rescue medication as described in the following list) will be prohibited from the Screening Visit (Visit 1) and onward for the duration of the study (including 2 weeks post-treatment). This includes the following:

- Lactulose
- Stimulant laxatives, including senna (Ex-Lax®) and sennosides (e.g., Senokot®, cascara sagrada, anthraquinones, castor oil, aloe, or others (if unsure, clinical sites to discuss with medical monitor (MM)).
- Osmotic laxatives (e.g., polyethylene glycol 3350 [MiraLAX®], magnesium hydroxide [Milk of Magnesia®], magnesium sulfate [Epsom Salts®] sodium biphosphate [Phospho-Soda®], saline laxatives [magnesium citrate], glycerine suppositories, glucitol [Sorbitol®] lactulose)
- Bisacodyl (e.g., Dulcolax®, Carter's Little Pills®, Alophen®, Correctol®) and other diphenylmethane laxatives (phenolphthalein). Note: See rescue medication exception in **Section 3.3.1**
- Stool softeners (docusate sodium, e.g., Colace®)

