3.2 EXCLUSION CRITERIA

A patient will be excluded from the study if he or she meets any of the following criteria:

1. The patient has a mental age <4 years in the investigator's opinion;
2. The patient has previously been diagnosed with anorectal malformations, neurological deficits, or anatomical anomalies that would constitute a predisposition to constipation;
3. The patient currently requires iron supplements, amitriptyline, or other tricyclic antidepressants for depression, opioid-containing medications or compounds for pain, or has other conditions that require medications known to cause constipation. A patient with an onset of constipation prior to the use of these medications and who has been on a stable dose for at least 8 weeks prior to Screening might be considered eligible for this study if the investigator deems these medications do not significantly contribute to the patient's constipation. Screening of these patients needs to be approved by the medical monitor and the sponsor;
4. The patient is pregnant or lactating;
5. Females age 12 to < 18 or females age 6 to 11 of childbearing potential (defined as post menarche) who does not agree to practice one of the following medically acceptable methods of birth control throughout the study;
 - Hormonal methods such as oral, implantable, injectable, vaginal ring, or transdermal contraceptives for a minimum of 1 full cycle (based on the patient's usual menstrual cycle period) before study drug administration.
 - Total abstinence from sexual intercourse (since the last menses before study drug administration
 - Intrauterine device.
 - Double-barrier method (condoms, sponge, or diaphragm with spermicidal jellies or cream.

6. The patient follows a diet not considered normal by the investigator for the patient's age, relative to variety of food, caloric content, and quantity. The patient must have been on a stable diet for at least 30 days prior to Screening;
7. The patient's mobility or normal exercise tolerance is compromised in the investigator's opinion;
8. The patient has a history of an eating disorder;

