4.1.3 Previous Medications and Diet

At the Screening Visit (Visit 1), the clinical site will ensure the patient is not or has not been on prohibited medications, supplements or investigational agents during the specified time (see **Section 3.3.2**). If the patient has used a prohibited medication within the proscribed time period prior to Visit 1, the site needs to ensure that the required washout period for the medication is completed before commencement of the 2-week baseline diary assessments. Previous medications will be documented as described in **Section 3.3**.

The diet history of each patient will be reviewed at Screening (Visit 1) to determine if the patient has been on a stable diet for the last 30 days, and whether the patient agrees to remain on that diet for the duration of the study.

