5.2 PROCEDURES BY VISIT

5.2.1 Visit 1: Screening (Day -28)

The patient must be screened within 28 days before the randomization visit in the study. A 3-day window is allowed to complete all procedures of the Screening visit. The last 14 days prior to randomization will be used as the patient's baseline electronic diary assessment.

The following will be completed at the Screening Visit:

- Obtain informed consent/assent. The parent/guardian/LAR must provide written informed consent and the patient must provide written or verbal assent as required by the IRB providing oversight.
- Assign a unique patient number. Unique patient numbers will begin with the clinical site number, e.g., 001 followed by a 3-digit number. Unique patient numbers will be assigned sequentially by the IWRS system accessed by the clinical site personnel. This unique patient number will be kept for the duration of the study. Patients who discontinue from the study before randomization will retain their unique patient number (i.e., numbers from screen fail patients will NOT be reassigned).
- Assess willingness and ability to maintain a stable diet and fiber supplements (if applicable) for the study period and to comply with not using laxatives except for the rescue medication provided as part of the study.
- Determine eligibility, based on Rome IV criteria for child/adolescent IBS and IBS-C. (**Appendix A**)
- Review inclusion/exclusion criteria.
- Collect demographic information.
- Record medical history, including GI and bowel habit history.
- Record prior and concomitant medications, vitamins, nutritional supplements, and dietary history.
- Perform urine pregnancy test for females age 6 to 11 that are of child-bearing potential and all females 12 to < 18.
- Perform urine screen for opioids (see **Section 4.3.2** for details).
- Collect blood and urine samples for safety laboratory tests (serum chemistry, including thyroid-stimulating hormone [TSH], hematology, and urinalysis).
- Measure vital signs (body temperature and seated blood pressure, heart rate, respiration).
- Perform a physical examination, including measurement of body weight and height.
- Perform 12-lead ECG in the semi-recumbent or supine position.
- For a child patient (6 to 11 years of age), determine and document based on the child's level of understanding, whether the child or caregiver will be responsible for recording of diary responses.

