8.4.3 Baseline Definition

For each safety parameter, the most recent valid assessment recorded before randomization will be used as the baseline for all analyses of that safety parameter.

For efficacy parameters, the baseline values will be derived from data collected in the 2-week electronic diary assessment at the end of the Screening Period (baseline). The last 14 days of diary entries prior to Day 1 will be the default standard for derivation of these values.

The baseline BM (SBM, CSBM) weekly rate will be the weekly average number of BMs (SBMs, CSBMs) recorded during the 2-week baseline assessment period; similarly, for frequency of abdominal pain and abdominal discomfort, frequency of fecal incontinence, frequency of defecation pain, and frequency of large diameter stools. Baseline stool consistency, severity of abdominal pain, abdominal discomfort, and severity of defecation pain will be calculated as follows: for each week of the baseline assessment, the weekly average is the sum of the non-missing scores recorded during the week divided by the total number of non-missing scores recorded during that week; the baseline is then equal to one-half of the sum of the two weekly average scores.

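### Opioid or antibiotic use permitted during screening can fall inside the 14-day baseline diary, because the drug-free gap is counted to randomization and not to the start of that diary

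*Combined protocol and SAP*

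**What the plan says.** Protocol section 3.3.2 generally prohibits opioids and antibiotics but makes an exception: "short-term (< 15 days) use of opioids or antibiotics for the treatment of AEs or intercurrent illness may be administered during the Screening Period", provided the use is reported. If such a drug has to be started in screening, "Visit 2 may be delayed allowing for discontinuation of these medications at least 3 days before randomization".

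The measurement window is fixed elsewhere. Section 5.2.1: "The last 14 days prior to randomization will be used as the patient's baseline electronic diary assessment". Section 5.2.2 has the IWRS decide diary eligibility from the same 14 days. Section 8.4.3, repeated in SAP section 3.3.7, says of the efficacy baseline: "The last 14 days of diary entries prior to Day 1 will be the default standard for derivation of these values". For the primary variable, "The baseline BM (SBM, CSBM) weekly rate will be the weekly average number of BMs (SBMs, CSBMs) recorded during the 2-week baseline assessment period".

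For prohibited drugs used before Visit 1, section 4.1.3 has the site make sure that the "required washout period for the medication is completed before commencement of the 2-week baseline diary assessments".

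On bowel effects, exclusion criterion 3 (section 3.2) covers a patient who needs "opioid-containing medications or compounds for pain, or has other conditions that require medications known to cause constipation", and section 3.3.2 lists opiates among the antidiarrheal agents.

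On timing, section 5.2.1 says "The patient must be screened within 28 days before the randomization visit in the study", while section 1 calls 28 days the ideal interval.

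**The concern.** The two-week diary has two jobs: it confirms that the child meets the SBM, CSBM, pain and stool-form limits, and it supplies the baseline for the primary endpoint. Section 4.1.3 protects it from drugs taken before Visit 1. Section 3.3.2 does not protect it from the same drugs started later, nearer to the window or inside it, because its gap is tied to randomization.

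For opioids, the protocol's own classification implies fewer bowel movements on the exposed days. A child over the SBM or CSBM limit could then qualify, and an eligible child could have a baseline that is too low. When the drug effect ends, the SBM count rises whatever the assigned arm.

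The contrast with exclusion 3 is marked. A child on a long-term opioid needs constipation that began before its use, a stable dose for 8 weeks, the investigator's judgment, and approval by the medical monitor and the sponsor. A new opioid inside the baseline window need only be reported.

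**Working it through.** **1. The plan's own figure.** Inputs from section 8.2: 102 and 34 patients, difference 1.5 SBMs/week, SDs 3.5 and 2.3. Alpha is 0.05 two-sided, from section 8.4 (the 0.05% printed in 8.2 would give 26.6% power, so it looks like a slip).

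SE = sqrt(3.5²/102 + 2.3²/34) = 0.525. Power = Phi(1.5/0.525 - 1.96) = 81.5%, as stated.

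**2. Baseline days on drug.** Baseline is days -14 to -1 (SAP section 3.3.7 has no day 0). A course under 15 days lasts at most 14 days.

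| Reading of section 3.3.2 | Last dose | Baseline days on drug | First week / second week |
|---|---|---|---|
| Three full drug-free days | day -4 | 11 of 14 (79%) | 7 / 4 |
| Last dose three calendar days before Day 1 | day -3 | 12 of 14 | 7 / 5 |
| Visit 2 not delayed (the delay is worded as optional) | day -1 | 14 of 14 | 7 / 7 |

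If the section 4.1.3 standard also covered drugs started in screening, the count would be 0 of 14.

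**3. Effect on one exposed child.** The documents give no size for the opioid effect, so I assume that the SBM rate falls by a fraction r on drug and recovers at once. With 11 days exposed:

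- First week = rate × (1 - r); second week = rate × (4(1 - r) + 3)/7.
- The 14-day baseline falls by 11r/14: 7.9%, 19.6% and 39.3% for r = 10%, 25% and 50%. At a habitual 3/week that is 0.24, 0.59 and 1.18 SBMs/week.
- Against the limit of 6 SBMs in either week (exclusion 21), a child at 7/week is expected to show 6.3 and 6.6 at r = 10% (fails), and 5.25 and 6.0 at r = 25% (passes).
- A child at 8/week shows 6.0 and 6.9 at r = 25% (fails), and 4.0 and 5.7 at r = 50% (passes).

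These are expected counts against the SBM limit only.

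**4. Effect on the trial.** Assume a share q = 2% to 10% exposed, balanced across arms, with an average shift s = 0.6 to 2.4 SBMs/week among them. I keep 102 and 34 so that the comparison is with the stated 81.5%.

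- Mean change from baseline in each arm rises by q × s: from 0.02 × 0.6 = 0.01 to 0.10 × 2.4 = 0.24.
- Added variance is q(1 - q)s². At the worst corner it is 0.10 × 0.90 × 2.4² = 0.518. SE = sqrt((12.25 + 0.518)/102 + (5.29 + 0.518)/34) = 0.544, and power = Phi(1.5/0.544 - 1.96) = 78.7%.
- At the mildest corner power stays at 81.5% after rounding.

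This ignores baseline adjustment and any smaller drug effect in children who should not have qualified.

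**5. Is the exposure caught elsewhere?** The SBM definition adjusts for laxatives only. Section 5.2.2 relieves site staff of judging diary eligibility. SAP section 4.2 has no per-protocol criterion aimed at this use. Section 3.3 asks for medication dates to month and year at minimum, and SAP section 3.3.5 sets a missing end day to the end of the month, so exposed diary days may not be identifiable afterwards.

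**The case against.** The two washout rules cover different situations. Section 4.1.3 concerns use before Visit 1; section 3.3.2 concerns illness that arises during screening. That stands: it is a difference in standard, not a flat contradiction. It does not explain why the later exposure should have the weaker rule.

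Safeguards exist. A positive urine opioid screen at Visit 2 is an automatic screen failure, entry criteria are reviewed again then, exclusions 9 and 10 let the investigator refuse a child whose illness or medication would interfere with assessments or data collection, and the use must be reported. These lower the risk but do not remove it. The screen covers methadone, morphine and oxycodone only and reflects status at Visit 2, and the exclusions are discretionary. The word default in section 8.4.3 leaves room for another window, but none is defined.

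Passing the SBM limit is not enough to enter. The child must also meet Rome IV IBS-C, stay under 3 CSBMs and average at least 3 for worst pain in each baseline week. An opioid taken for pain would tend to lower that score. This stands, and it is why the figures in step 3 show possible, not likely, entry.

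The 28-day limit might seem to push sites toward the shortest gap. The documents do not show this: section 3.3.2 allows a delay and section 1 calls 28 days ideal.

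**Conclusion.** The gap is real. As written, the plan lets 11, 12 or 14 of the 14 baseline days be recorded on a permitted opioid or antibiotic, depending on how the 3-day provision is read. For opioids, the protocol's own classification makes distortion of an exposed child's eligibility and SBM baseline plausible. The consequences are possible ineligible entrants, a noisier baseline covariate and an inflated within-arm change.

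A reader might infer more than the documents support:

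- *That the treatment comparison is biased.* Exposure precedes randomization, so it is balanced in expectation, and the primary model adjusts for baseline.
- *That 11 days is the maximum.* It holds only if three full drug-free days are kept.
- *That antibiotics distort the diary in a known direction.* The documents prohibit them but state no bowel effect.
- *That a shift of 1 to 3 SBMs/week in one child rivals the 1.5 design effect.* One is an individual baseline error, the other a difference between arm means.

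The number of exposed children is not given and is probably small. Under the assumed ranges the trial-level effect is at most 0.24 SBMs/week in each arm's change and a fall in power from 81.5% to 78.7%. This is an inexpensive improvement to make, not a threat to the trial's conclusion.

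**What to change.** Reconcile protocol sections 3.3.2, 4.1.3, 5.2.1 and 8.4.3, with SAP section 3.3.7, so that one rule states which diary days may count toward eligibility and baseline after permitted use in screening. The IWRS should apply the same rule. Word the screening interval in 5.2.1 so that it accommodates the delay that 3.3.2 already allows. The washout length is for the sponsor to settle; nothing here changes whether or when a child receives the medication.

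Record full start and stop dates for opioids and antibiotics taken in screening. In the SAP, flag patients with any baseline day on drug, report their number by arm, and repeat the primary analysis without them.

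The cost is a few sentences, some IWRS and analysis programming, and two complete dates per course. If the sponsor chose to take the whole baseline after the present 3-day gap, the earliest randomization would move from 3 to 3 + 14 = 17 days after stopping, so up to about 14 more screening days for the few patients concerned.
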